Trial design: Adults and adolescents (post puberty) with SCD who are treated with outpatient red cell transfusions will be randomized in blocks of 5 (S. Piantadosi block randomization software, 2010) to receive ≥ 30 day or ≤ 10 day old units for 3 months (3 consecutive transfusion events). **The study statistician** will provide the blood bank with the schema who will then be responsible for providing the units for these subjects. Participants and all other investigators will be blinded to treatment assignment.

Two baseline venous blood samples will be obtained to be used as a baseline measurement of the patients underlying inflammatory status. The first will be drawn about 1- week prior to the first randomized transfusion, and the second sample just prior to the first randomized transfusion. Subjects will be asked to hold their iron chelation 72 hours before the study transfusion. Pre-transfusion, sterile samples will be extracted from red cell units. Patient venous blood samples will be also obtained 2 hours post transfusion, 24 hours post-transfusion, and 2 weeks post-transfusion (**Table 1**). Participants will complete standardized diaries daily to document symptoms of infection, SCD pain, medications and emergency department (ED) or hospital use. Diaries will be collected and participants will be assessed with each transfusion encounter, up to 3 transfusion events, and 4 weeks after the last transfusion. To ensure compliance, coordinators will

contact subjects regularly to remind them to complete diaries. All data will be captured with standardized case report forms and entered into an electronic database.

Subject Recruitment and Anticipated Numbers: We intend to recruit and enroll 40 subjects. Participants will be recruited from the Adult SCD Clinic at UNC and Emory/Grady Health System. We expect that UNC will recruit between 5-10 subjects over the next 2 years (15 subjects have already been enrolled at Medical College of Wisconsin), and Emory will recruit between 10-20 subjects to reach the study goal of 40 randomized subjects.

Subject Inclusion/exclusion criteria:

Inclusion criteria:

- 1) Ages 16 to 60 years old
- 2) Subject must have sickle cell anemia confirmed by hemoglobin analysis
- 3) Must be receiving red cell transfusion therapy
- 4) Must be outpatient at the time of study transfusions

Exclusion criteria:

- 1) History of severe reactions to transfusion therapy
- 2) Receive red cell transfusions that are crossmatch incompatible

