4.2 Stratification and Randomization

Subjects will be randomized to receive RBCs stored either ≤ 10 days at time of transfusion or ≥ 30 days at the time of transfusion. Storage arm assignment applies to up to 3 consecutive outpatient transfusions, beginning at the time of randomization and continuing through the end of the 3rd randomized outpatient transfusion. Randomization assignment can occur at any time between the date of consent till 2-3 days prior to the first study transfusion. Only the transfusion service will have access to the randomization assignment as designated by the study biostatistician.

Due to the pilot nature of this study, randomization will not be stratified by gender, age, ethnicity, or hemoglobinopathy type.

For the first study transfusion, after the number of units requested for crossmatch is known, but no earlier than 2-3 calendar days before transfusion, a study staff member will contact the institution's transfusion service to determine whether the transfusion service has enough suitable units stored ≤ 10 days and ≥ 30 days to meet the crossmatch request for this subject.

If there is not sufficient inventory to meet the randomization criteria, the subject's study participation will be postponed, and unit availability will be assessed again prior to their next outpatient transfusion.

Once the subject has received their first study transfusion, the remaining 2 outpatient study transfusion events will occur regardless of whether the transfusion service can meet the transfusion needs of the study.

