5. INTERVENTIONS

5.1 Preparation

In Section 5 of this protocol, the term "study RBC units" includes all RBC units provided to a randomized subject, beginning at the time of the first study transfusion and continuing through the end of study. Transfusions will always be ordered based on patient need, following all institutional policies and practices. The decision to order (or not order) an RBC transfusion is not dictated in any way by the study protocol

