10.2.1 Primary Outcome Analysis

Key variables of interest:

PS – Measured as a percent of RBC positive

PE – Measured as a percent of RBC positive

Microparticles – Measured by number positive per microliter
CD62L – Measured as percent of monocytes positive
Plasma free hemoglobin – Measured as mg/dL
Non-transferrin bound iron – Measured as mg/dL
Rate of clinical infections – Measured as number per days on study

Aim 1:

The primary outcome measure is the proportion of biochemically old red cell units. Previous studies and our own work have suggested that PS, PE, and microparticles increase in a sigmoidal fashion over time.^{7,10} For this study, the cut-off for a biologically old unit would be the point at which the sigmoidal curve enters its log phase, which for PE, PS, and microparticles will be the mean value at day 21, or 8%, 3%, and 3/ μ L respectively based on these preliminary studies. This cutoff is biologically meaningful and is supported temporally by the metabolic changes that occur with red cell storage.¹¹⁹ Consequently, biochemically old units will be defined as having either a surface PE, surface PS, or a microparticle concentrations \geq the *a priori*-defined cutoff. We will compare the transfusions provided to the two groups (the proportion of biochemically old units when stored \geq 30 days compared to when stored \leq 10 days) using a Fisher exact test at an alpha of 0.05. Power: With a total sample size of 40 patients (20 in each group), we will have at least 80% power ($\alpha=0.05$) to detect a difference of at least 47% between the two randomized groups for biochemically old red cell units (close to a 100% difference is expected).

Exploratory: We will calculate the mean, minimum, and maximum levels of PS, PE, and microparticles for each study group, and we will compare the secondary outcome measures of plasma free hemoglobin, heme, and NTBI and also PS, PE, and microparticle concentrations using a two sided two sample t-test at an alpha of 0.05. We will also plan for auxiliary analyses that characterize the relationship between the PS level and the age (days) of the RBC units. This analysis will focus on estimation of the mean PS, PE, and microparticle level as a function of age (days), visualization of the data values, estimation of correlation coefficients, and evaluation of how well age (days) predicts PS, PE, and microparticle levels.

Aim 2:

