The primary outcome measure is the change in CD62L (activated) circulating monocyte/macrophage MFI at 2 hours post-transfusion compared to the subject pre-transfusion. We will compare the two groups (\geq 30 day-old compared to \leq 10 day-old unit exposure) using a two sample two-sided t-test of the log at an alpha of 0.05. Power: We will have at least 80% power to detect a change in the ratio of 1.35 post-transfusion if the variability is similar to that seen in our preliminary data.

Exploratory: We will use a general(ized) linear model to include biochemically old units transfused (Aim 1 outcome), regardless of unit age, as a covariate in our analysis. Other co-variates in this model will include free heme, cell free hemoglobin, and NTBI. We will similarly compare other obtained activation measures as outcomes: activation markers for monocytes, neutrophils (as listed in section 6) and measured plasma cytokine

concentrations (section 6). We will also plan for auxiliary analyses of the outcome variables in which the explanatory variable is the age (days) of the RBC units --to characterize the degree to which age (days) can accurately predict the clinical and physiologic outcome measures defined. Lastly, as an exploratory aim, we will evaluate the *in vivo* change in recipient red cell PE/PS positivity at 2 and 24 hours post transfusion.

Aim 3:

The primary outcome variable is the rate of post-transfusion infections in the patient. The primary estimand is the treatment effect defined as the difference between the regimen-specific proportions of patients in the target populations that would experience post-transfusion infections. This population parameter will be estimated as a function of the proportions observed in the sample of patients studied. The point estimate will be reported along with the corresponding 95% confidence interval estimate. The presence of an indwelling catheter will be used as a key co-variate in this analysis. *Power:* A difference of 20% will be of clinical interest. We do not expect to have adequate power for this pilot study but at an alpha of 0.05 with 20 subjects in each group we will be able to detect a difference of 47% between the proportions.

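### Does Aim 3 need a different infection measure because the outcome is listed per days on study while the estimand is a proportion of patients with no stated window?

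*Combined protocol and SAP*

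**What the plan says.** The list of key variables in Section 10.2.1 gives the rate of clinical infections as "Measured as number per days on study". The Aim 3 paragraph also calls the outcome a rate, then declares: "The primary estimand is the treatment effect defined as the difference between the regimen-specific proportions of patients in the target populations". The estimator is a function of the observed proportions, reported with a 95% confidence interval. The power statement (47% with 20 per group) is for proportions too.

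On the start of the period, Section 4.2 says "Storage arm assignment applies to up to 3 consecutive outpatient transfusions, beginning at the time of randomization", and also "Randomization assignment can occur at any time between the date of consent till 2-3 days prior to the first study transfusion". If suitable units are lacking, "study participation will be postponed, and unit availability will be assessed again prior to their next outpatient transfusion". Section 5.1 defines study units as those provided "beginning at the time of the first study transfusion and continuing through the end of study". Sections 4.1 and 4.3 tie the start of the study to an outpatient transfusion visit; Section 4.3 moves it to the next visit if stock is short.

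On the end, the Synopsis has diaries and assessments at each encounter, "up to 3 transfusion events, and 4 weeks after the last transfusion", and Table 1 has an End of Study column that includes the diary. Section 6.7 item 1 ends participation when the three transfusions are complete. The Synopsis and the Aim 3 exploratory text speak of 3 months. Section 6.8 defines chronic transfusion by a 3-8 week schedule, and Section 1 calls it typically monthly.

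**The concern.** A rate counts repeat infections and divides by time observed. A proportion of patients does neither. A proportion also has little meaning without its time span, and the Aim 3 text gives none. With 3-8 week spacing, patients who complete the same three transfusions are observed for quite different lengths of time. A crude proportion treats them alike.

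Three things could be at stake. The primary quantity might be ambiguous. The arm comparison might be distorted if follow-up differed by arm. And the infection figure might be hard to carry into the larger trial that Section 2.1 says these data will inform. A window chosen after the data are seen would add some freedom to the analysis.

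**Working it through.** **Which quantity was sized.** Inputs from Section 10.2.1: 20 per arm, alpha 0.05. The 80% power is taken from Aim 1, which gives the same 47% and the same n. The lower-arm proportion is not in the documents, so it is assumed. Exact two-sided Fisher power gives a detectable difference of 47.3 points at a lower proportion of 20%, and 31.4 to 48.3 points over lower proportions of 0-30%. The plan's 47 is therefore a two-proportion figure, in line with the declared estimand.

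**Window.** From the first study transfusion to 4 weeks after the third, with spacing s weeks, the length is 2s + 4:
- s = 3: 10 weeks
- s = 4 (monthly): 12 weeks
- s = 8: 20 weeks

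Ending at the third transfusion gives 2s = 6 to 16 weeks. At monthly spacing, 12 weeks is close to the plan's 3 months (13 weeks).

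**How much the window matters.** Assume a constant 0.03 infections per week; no rate is given in the documents. Risk = 1 − exp(−0.03 × weeks): 26% at 10 weeks, 32% at 13, 45% at 20. The level does depend on the window.

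**Arm comparison.** Assume follow-up uniform on 10-20 weeks (SD 10/√12 = 2.89).
- Chance difference between arms in mean follow-up: SE = 2.89 × √(2/20) = 0.9 weeks.
- Means of 14 v 12 weeks: exp(−0.36) − exp(−0.42) = 4 points (1.8 to 5.5 for 0.01 to 0.06 per week).
- Means of 16 v 12 weeks: exp(−0.36) − exp(−0.48) = 8 points.
- Half-width of the 95% interval at a proportion of 0.32: 1.96 × √(2 × 0.32 × 0.68/20) = 0.29, or 29 points.

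Nothing in the design creates such gaps. Section 4.2 checks stock of both unit ages before the first study transfusion, so postponement does not depend on arm. After that, Sections 4.2, 5.1.2 and 5.1.3 have transfusions go ahead whether or not units of the right age are available.

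**Planning a larger trial.** If only a bare 30% were known, the implied rate would be −ln(0.7)/10 = 0.036 per week or −ln(0.7)/20 = 0.018. A 26-week trial would then expect 60% or 37%. But Section 6.5 records transfusion times, so mean follow-up will be known. With 0.03 per week and follow-up uniform on 10-20 weeks:
- Crude proportion = 1 − [exp(−0.3) − exp(−0.6)]/0.3 = 36%.
- Recovered rate = −ln(0.64)/15 = 0.0298 per week.
- Projection to 26 weeks = 53.9%, against a true 1 − exp(−0.78) = 54.2%.

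**The alternative: a Kaplan-Meier difference at a fixed calendar horizon.** In simulation with 20 per arm and 0.06 v 0.02 per week, power is 55% for the crude difference, 47% at a 10-week horizon and 53% at 13 weeks.

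Now suppose risk follows transfusions: 0.12 infections per transfusion, spread evenly over the next 2 to 4 weeks, with transfusions at 0, 6, 12 weeks in one arm and 0, 4, 8 in the other. Risk per course is 1 − exp(−0.36) = 30% in both arms.
- At 10 weeks with a 2-week spread, the slower arm has accrued 0.24 and the faster 0.36: 21.3% v 30.2%, a spurious 8.9 points.
- At 13 weeks with the same spread, 0.30 v 0.36: 25.9% v 30.2%, a spurious 4.3 points.
- The 4-week spread falls between these.

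**The case for a change.** The strongest case for a change is that a proportion with no time span is an incomplete estimand, and that settling the span is cheap and best done before the data are seen. Section 6.7 item 1 does not agree with the 4-week follow-up in the Synopsis. Section 10.2 expects no drop-outs and does not say how an infection-free patient who leaves early is counted. Section 10.2 also includes everyone randomized, and a patient who is randomized but never transfused has no time after transfusion. All of that is true as a description of the text.

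The part about the start is weaker. Section 4.2 says how long the arm assignment applies and Section 5.1 defines a term for study units; neither defines infection follow-up. Sections 4.1 and 4.3 place the start at the study transfusion visit, and the Aim 3 outcome is infection after transfusion. One postponement of s weeks would lengthen the period to 3s + 4 = 13 to 28 weeks and lower the rate by 1 − (2s + 4)/(3s + 4) = 23% to 29%. That happens only if the waiting days enter the denominator while infections in them are left out of the numerator, which no section asks for.

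Early leavers are not ignored: Section 10.2 provides for an examination of missingness, multiple imputation and sensitivity analyses. If 15% left early, at times spread evenly over their follow-up, and were counted as uninfected, the 36% above would become 33.5%. That is a small shift and applies to both arms.

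What stands is missing detail and loose use of the word rate in Sections 9 and 10.2.1.

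**Conclusion.** No change to the plan is needed. Aim 3 declares a difference in proportions as primary, and its sizing matches. Risk per three-transfusion course is a legitimate quantity for a hypothesis about transfused units. The per-days listing is a natural supportive summary, and it supplies the follow-up time that a later planner needs. The best-supported window can be read from the plan and derived from recorded dates. Section 6.7 item 1 and the Synopsis still have to be reconciled on when participation ends, which is a matter of wording.

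No bias between arms is shown. The plausible shifts (about 4 points for a 2-week gap in mean follow-up) are small beside a 29-point half-width in an aim that the plan itself calls underpowered. A calendar horizon would exchange one limitation for others: power of 47% or 53% instead of 55%, and a possible spurious difference of 4 to 9 points. It may serve as a sensitivity analysis but corrects nothing.

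The conclusion rests on an assumed constant infection rate (0.01 to 0.06 per week), an assumed spread of follow-up, and follow-up that does not depend on arm. If early departures turned out clearly unequal between arms, the crude proportion would need closer scrutiny.

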2.2 Secondary Aims

Aim 1:

To explore whether: ≥ 30 day-old units will have significantly greater mean 1) phosphatidylethanolamine expression, 2) cell free hemoglobin concentration, 3) cell free heme expression, and/or 4) NTBI expression in comparison to ≤ 10 day-old units.

Aim 2:

To explore whether:

- 1) Those administered ≥ 30 day-old units will have a greater increase in the number of activated monocytes or neutrophils as defined by flow cytometry markers of activation at 2 or 24 hours post-transfusion compared to those administered ≤ 10 day units.
- 2) Those administered ≥ 30 day-old day units will have a greater increase in the concentration of NTBI, cell free hemoglobin, and free heme, compared to those administered ≤ 10 day-old units at 2 or 24 hours post transfusion.
- 3) Recipient RBC PS, PE, and microparticle expression will increase more between 2 and 24 hours after receiving ≥ 30 day-old units than after receiving ≤ 10 day units.

Aim 3:

To explore whether those administered ≥ 30 day-old units will have a more rapid increase in the concentration of HbS% and a more rapid decrease in hemoglobin over time compared to those administered ≤ 10 day-old units.

Aim 4:

To explore whether those administered ≥ 30 day-old units will have a significantly different RBC metabolomic profile 2 and 24 hours post transfusion than those provided ≤ 10 day-old units.

Aim 5:

We will address aspects of study feasibility, such as subject drop-out, rates of missing data, and the confidence intervals/precision of our recorded variables, including PS, PE, microparticles, CD62L, and the other recorded clinical variables.

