5.2 Administration

RBC units will be administered according to local institutional policy and safety standards as ordered by the medical team for patient care needs.

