6.5 RBC Transfusions

The following data will be collected for each RBC unit ordered for the subject while on study:

- Unit ID number
- Source of unit (apheresis or whole blood collection)
- Blood group of unit (ABO and Rh)
- Leukoreduction status
- Irradiation status
- Volume reduction/washed unit status
- Storage medium (AS1, AS3, or AS5)
- Antigens matched (D, Cc, Ee, Kk, or other)
- Collection or expiration date (specifically recorded by the blood bank to maintain study coordinator blinding)
- Start time and end time of transfusion

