Exploratory: We will explore the relationship of blood age and transfusion of biochemically old red cell units on the change in Hb and HbS% over time, daily pain scores (0-10 as an ordinal scale), opioid use and dose, ED and hospitalization rate, infection symptoms, new alloantibody formation, and antibiotic use during the 3-month study period. We will compare groups using a Fisher exact test. We will also plan for auxiliary analyses of the outcome variables in which the explanatory variable is the age (days) of the RBC units --to characterize the degree to which age (days) can accurately predict the clinical and physiologic outcome measures defined.

AIM 4:

We will calculate the mean, median, minimum, and maximum levels of each metabolic compound analyzed by [name] in his laboratory at the University of Colorado. Analysis tools and methods will be determined by his research team, and will focus on changes in the patient and the unit pre and post transfusion.

AIM 5:

Feasibility Analysis: We will assess important variables necessary to develop a future larger clinical trial on this subject. Areas that we will investigate during the course of this trial will include frequency and content of missing data, subject drop out rates, and estimates of outcome measure precision. For this study, we will evaluate the number of males, females, and adolescents that enroll in the study to inform future studies. We do not expect there to be differences in the key outcomes based on these variables, and plan to analyze all 40 subjects together as one cohort, but differences by age and gender will be evaluated and considered.

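### Secondary Aim 3 leaves Hb and HbS% change over time undefined across need-ordered transfusions, so a cross-transfusion comparison would lean toward no difference; within-interval change avoids most of this

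*Combined protocol and SAP*

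**What the plan says.** Section 2.2, Secondary Aim 3, asks whether recipients of units stored 30 days or longer show "a more rapid increase in the concentration of HbS% and a more rapid decrease in hemoglobin over time" than recipients of units stored 10 days or less.

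The matching analysis is the exploratory paragraph for Aim 3 in section 10.2.1: "We will explore the relationship of blood age and transfusion of biochemically old red cell units on the change in Hb and HbS% over time". Hb and HbS% head a list that also covers pain scores, opioid use, admissions and antibiotics over the 3-month study period. The one group comparison named for the whole list is: "We will compare groups using a Fisher exact test". No reference sample, time window or covariate is given for Hb or HbS%.

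On ordering, section 5.1 states "Transfusions will always be ordered based on patient need, following all institutional policies and practices" and "The decision to order (or not order) an RBC transfusion is not dictated in any way by the study protocol". Section 5.2 has units given "as ordered by the medical team for patient care needs". Section 6.8 defines chronic transfusion as a 3 to 8 week schedule.

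On data, Table 1 marks CBC and HbS% before, 24 hours after and 2 weeks after every transfusion, and neither at end of study. Section 6.2 allows 2 days either side of the 2-week sample. Section 6.5 opens with "The following data will be collected for each RBC unit ordered for the subject while on study" and includes start and end times. Unit volume is not in its list.

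**The concern.** Transfusion raises Hb and lowers HbS%, as section 1 of the protocol says. If a patient's Hb falls faster after old units, that patient arrives lower at the next visit and may be ordered more units, be brought in sooner, or be transfused between visits. Each response pushes Hb back up and HbS% back down. The compensation is larger in whichever arm declines faster, so a contrast of levels or trend across transfusions is pulled toward no difference.

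Nothing in section 10.2 deals with this. The random-effects model appears there as a remedy for missing data. The subanalysis removes transfusions with units of the wrong age, not readings affected by larger or extra transfusions. The covariates listed for Aim 2 do not include units given. A Fisher exact test does not estimate a rate of decline at all.

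At stake is the use of these data to design the larger trial that section 2.1 foresees. An attenuated Hb effect would be reported as inconclusive under section 10.2, and any arm difference in blood use would go unreported.

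**Working it through.** The documents give no SD, effect size, target or power for Hb or HbS%, so there is no stated figure to reproduce. **All Hb inputs below are assumptions that illustrate the mechanism. None is a proposal for care.** HbS% was not simulated; the argument for it is directional only.

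**1. Levels across transfusions, by hand.** Assume a 4-week interval and an Hb decline of 0.40 g/dL per week (young units) or 0.50 (old units), an arm difference of 0.10 per week. Let g be the share of any pre-transfusion shortfall that ordering corrects. Let D(k) be the old-minus-young difference before transfusion k, with D(1) = 0.

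- 24 hours after transfusion k: (1 − g) × D(k)
- 2 weeks after: (1 − g) × D(k) − 2 × 0.10
- Before the next transfusion: D(k+1) = (1 − g) × D(k) − 4 × 0.10

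For g = 0.5: D(2) = −0.4 and D(3) = 0.5 × (−0.4) − 0.4 = −0.6. At 24 hours after transfusion 3 the difference is 0.5 × (−0.6) = −0.3, and at 2 weeks −0.3 − 0.2 = −0.5.

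| Difference at transfusion 3 (g/dL) | g = 0 | g = 0.5 | g = 1 |
|---|---|---|---|
| Before | −0.8 | −0.6 | −0.4 |
| 24 hours | −0.8 | −0.3 | 0.0 |
| 2 weeks | −1.0 | −0.5 | −0.2 |
| Change, 24 hours to 2 weeks | −0.2 | −0.2 | −0.2 |

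The level contrasts shrink as g rises. The within-interval contrast does not move.

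**2. Slope across all nine readings, by simulation.** Assumed: first pre-transfusion Hb mean 8.2, SD 0.7; +1 g/dL per unit; under titration, units equal 10 minus Hb, rounded, limited to 1 to 4; loss 0.05 against 0.07 g/dL per day, between-patient SD 0.015; measurement SD 0.3; 28-day interval; samples on days 0, 1, 14, 28, 29, 42, 56, 57 and 70; 200,000 patients per arm. The true slope difference is 0.020 per day.

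| Ordering at later visits | Share of true slope difference recovered |
|---|---|
| All titrated to Hb | about 23% (up to 28% with small coding differences) |
| Half titrated, otherwise first amount repeated | about 59% to 61% |
| A quarter titrated | about 79% |
| Fixed amount | 100% |

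The fixed-amount row is the control: it shows that the loss comes from need-based ordering. Under full titration, intervals of 21 to 56 days gave about 18% to 47%.

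The 24-hour to 2-week change spans 13 days, so the true difference is (0.07 − 0.05) × 13 = 0.26 g/dL. It was recovered in full in every row. Under full titration the old arm received about 1.9 units per visit from the second visit, against about 1.4.

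**3. Does the within-interval window close in time?** The 2-week sample falls on days 12 to 16. The shortest routine interval is 3 weeks, day 21. The window therefore closes before the next scheduled transfusion, and the first interval precedes any on-study feedback on ordering.

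**4. What that window misses.** If 10% of transfused cells in the old arm were cleared by 24 hours and decline was equal afterwards, a mean of about 1.8 units at +1 g/dL would leave Hb lower by 0.10 × 1.8 = 0.18 g/dL at 24 hours. The 24-hour to 2-week difference would be 0.00. The window also stops early: in a 28-day first interval the difference reaches 0.02 × 27 = 0.54 g/dL by the next visit, against 0.26 at 2 weeks.

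**The case against.** A reader might infer that any faster decline after old units is treated away and hidden. The documents do not support that. The 24-hour and 2-week samples are already scheduled after every transfusion, the first interval is free of on-study feedback, and unit counts and times are recorded. The signal is in the data; the plan does not commit to the contrast that preserves it.

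A reader might also infer that the plan intends one slope through all nine readings. No section says so. A more rapid fall could equally mean a fall after each transfusion. The gap is an undefined measure, not proof that the worst version is planned.

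The attenuation is also conditional. No section gives an Hb target, usual units per visit or a rate of extra transfusions, and ordering to need need not mean titrating to Hb. The 23% figure is one end of a range that reaches 100%.

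Finally, the within-interval measure has limits of its own. It skips first-day clearance, which matters because section 1 describes rapid phagocytosis. Adjusting for the 24-hour value would condition on something measured after randomisation. Dropping intervals with extra transfusions would select on a post-randomisation event. These objections stand, and they shape the fix.

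**Conclusion.** The concern holds in limited form. Need-based ordering outside protocol control, an undefined change over time and a Fisher exact test leave the Hb and HbS% comparison open to bias toward no difference if it is made on levels or trend across transfusions. Under the assumed inputs and a 28-day interval, the share of the true slope difference recovered runs from about 23% (every order titrated to Hb) through about 59% (half) to 100% (fixed amounts). Where this trial would fall cannot be read from the documents.

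The within-interval change recovers the full difference in these illustrations. That rests on two assumptions: no unscheduled transfusion falls between the two samples, and daily loss does not itself depend on the number of units given.

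The severity is minor to modest. The aim is exploratory, section 2.1 declares a feasibility study, and no primary aim or safety decision rests on this comparison.

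**What to change.** Amend the SAP wording for Secondary Aim 3; transfusion practice stays as it is.

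- **Measure:** change in Hb and in HbS% from the 24-hour to the 2-week sample after each study transfusion.
- **Model:** compare arms with a repeated-measures model over up to three intervals per patient, in place of the Fisher exact test. Adjust for the Hb or HbS% value before the first study transfusion, not for the 24-hour value.
- **First-day clearance:** report by arm the rise from the pre-transfusion to the 24-hour sample per unit given. Unit volume is not in the section 6.5 list, so this is per unit, not per mL.
- **Companion outcomes:** report units given per visit and interval length by arm.
- **Non-study transfusions between the two samples:** count them by arm and analyse those intervals both included and excluded.

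All samples and unit records needed are already scheduled, so the cost is wording and a little analysis time. The downside is that readings after 2 weeks carry less weight. The third interval has no later reading in any case, because Table 1 has no CBC or HbS% at end of study.
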